6.2 Assessors

Each site will have at least one blinded assessor who does not know the managing clinician's diagnosis. The independent assessor will examine the patient to record clinical diagnostic features as soon as possible after the clinician has made their assessment. The blinded assessor can be any individual included in the delegation log who is trained in vulval skin examination, and considered competent to do so by the Principal Investigator at the site. The individual is most likely to be, but not limited to the following groups: trainees, clinical fellows, or specialist nurses working alongside the managing clinician.

The research nurse/research support entering data into REDCap will be blinded to the consultant diagnosis.

6.3 Data entry

Data will be collected electronically by a research nurse/researcher blinded to the consultant's diagnosis using REDCap software. People with specific roles within the study will only have access to database forms relevant to their role meaning that blinding can be maintained within the database. In the event that the site do not have the ability to enter data directly into the REDCap database electronically, paper CRFs/worksheets have been created to ensure that relevant information is collected during the consultation. This includes the main CRF, the blinded assessment, and the managing clinician diagnosis. Data collected on paper will subsequently be transferred to REDCap by the local research team. These will be source documents that will be filed in the REDCap database and the investigator site file, and may also be stored as a copy in the medical notes.

6.4 Compliance

This is not an interventional study, so assessment of compliance is not applicable. If a participant does not have both the reference standard and the index test, they will be withdrawn from the study as it would not be possible to perform accuracy analysis.

6.5 Criteria for terminating the study

This is an observational study with no follow-up, so we do not anticipate the termination of the study for any reasons other than failure to recruit.

7 ANALYSES

7.1 Methods

[name] will undertake the analysis of the data under the supervision of [name] (Study Statistician).

Demographic data and participant characteristics will be analysed descriptively.

Stage 1

Developing a diagnostic prediction model:

i. Determining a predictive model of diagnostic criteria for vulval LS: All criteria identified will be included in a backward multivariable logistic regression model²² with exit criteria $p=0.157$.²³

ii. Quantifying the performance of the diagnostic prediction model: Explained variation will be measured by Cox-Snell R-squared. A calibration plot will assess how well predictions agree

with the observed data. Smoothed calibration curves will be plotted using a loess smoother.^{24,25} All data for model development will be included for use in internal-external cross validation across centres (alongside bootstrapping). Discrimination will be measured using the C statistic.²⁶ The model will be fitted to this dataset.

iii. Clinical utility: Thresholds on the calibration plot will be based on clinical utility i.e. what defines high risk and trade-offs between benefits and harm, defined by patients and doctors.

Stage 2

Model validation

Internal validation is essential to (i) obtain an unbiased estimate of the developed model's predictive performance, and (ii) adjust (shrink) the developed model for optimisation (if necessary). Bootstrapping and uniform shrinkage techniques will be used for analysis.

Missing data: Missing data is not anticipated as the diagnostic features will be assessed by clinical examination. There will be a 'yes' or 'no' answer recorded in the CRF for each criterion in each patient. Only if a participant declines to continue the examination or declines to be examined by the blinded assessor do we anticipate missing index-reference test data pairs. However, the sample size is increased by 10% to account for a maximum of 10% missing data. This will be monitored and if less than 10% data are missing, recruitment target will be reduced accordingly.

c. Inter-observer variability

The inter-observer reliability for assessing the individual diagnostic criteria on 20 cases and 20 non-cases from one of the sites will be calculated using the Kappa statistic. A value of Kappa >60% will be considered acceptable as 'good' agreement between observers.²⁷ At the site where these data are collected (Nottingham, lead site), there will be two independent assessors.

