3.3 Index and reference tests

3.3.1 Index test

The international electronic-Delphi exercise involving expert health professionals and patients (see section 1.3 for further detail) has identified a list of 17 diagnostic features which were agreed to be 'critical', or 'important but not critical' in the diagnosis of LS. The SHELLS diagnostic test accuracy study is using this list of 17 diagnostic features as the index test.

A diagnostic criteria assessment looking for the presence or absence of these 17 diagnostic features, using experience and clinical judgement, will be performed by an assessor blinded to the reference standard (specialist's diagnosis – see section 3.3.2).

List of diagnostic features to be assessed as part of the index test:

Critical:

- Changes in the anatomy of the genital area
- Response to topical corticosteroids
- Whiteness
- Itch
- Burying of the clitoral area

Important but not critical:

- Absence of vaginal involvement
- Fissuring
- Crinkly skin
- Bruising/bleeding under the skin
- Fissuring at the back entrance to the vagina
- Pain/soreness unrelated to sexual activity
- Pain/soreness related to sexual activity
- Skin thickening
- Loss of skin stretchiness

- Erosions
- Irritation
- Perianal fissure

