4.1 Duration of the study and participant involvement

Study Duration: The study will last for approximately 24 months overall, with the possibility for extension if participant recruitment is slow. Participant enrolment will begin once HRA and REC approvals have been obtained and all site approvals are in place.

Participant Duration: Participants will be involved at the point of consent to the study until the diagnostic criteria assessments have been completed. Participants will have one study visit that will last approximately 30 minutes. There will be no follow up appointments related to the study.

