5.2 Eligibility Criteria

5.2.1 Inclusion criteria

- Female
- ≥18 years of age
- New presentation to a specialist clinic (secondary care or community hub) with a vulval skin complaint

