6. REGIMEN

6.1 Patient pathway – Assessments

- Participants will receive a clinical assessment from their usual managing clinician as part of their usual outpatient appointment. This will involve a physical examination and routine clinical questions.
- A blinded assessor (for example, Trainee, Clinical Fellow, Specialist Nurse) will then examine the patient and record clinical diagnostic features on the CRF. A third assessor who is also blinded may also examine the patient at the Nottingham site. Participants can opt out of examination by two different professionals if they wish, but to participate in SHELLS they must agree to at least one additional examination.
- The blinded assessor will be asked to examine the patient without speaking to the managing clinician. The managing clinician will ensure that the clinical notes are closed

and unable to be viewed by the blinded assessor as they come in the room, and REDCap (Research Electronic Data Capture) will disable access to the clinician diagnosis by the blinded assessor. The patient will be advised not to give any information to the blinded assessor/s other than specific questions that are asked in relation to the research.

- The blinded assessment will ideally take place immediately after the managing clinician has examined the patient. This will prevent disruption of flow to patients coming through the clinic and it will prevent patients from having to get undressed twice.
 - However, we acknowledge that flexibility is required and each site may need to adapt their own flow for how the clinical assessments are performed, ensuring blinding of the additional assessor/s.
- Information collected by the research team (not the blinded assessor) for each participant will include:
 - Age
 - Ethnicity
 - Post code (for socioeconomic status)
 - Participant rating of the condition on the day of assessment
 - Physician global assessment of disease severity (assessed and recorded by managing clinician)
 - Symptom duration
 - Diagnosis of LS prior to clinic appointment
 - Previous diagnosis of a vulval condition (Y/N and what diagnosis)
 - Treatments received (Y/N and what treatment)
 - Treatment duration
 - Whether on active treatment at time of recruitment (Y/N)
 - Whether the patient has 'early or late' stage LS (assessed and recorded by managing clinician)
 - Presence or absence of each of the individual diagnostic features (Index test, see section 3.3.1)

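### A compulsory yes/no answer for every criterion has no place for patients in whom steroid response, or pain related to sexual activity, cannot be assessed

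*Protocol*

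**What the plan says.** Section 3.3.1 of the protocol lists 17 features as the index test. Five are classed as critical, and "Response to topical corticosteroids" is one of them. Pain or soreness related to sexual activity is among the other twelve. The assessor's task is described as "looking for the presence or absence of these 17 diagnostic features, using experience and clinical judgement".

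Section 7.1 gives the reason for expecting complete data: "Missing data is not anticipated as the diagnostic features will be assessed by clinical examination". It continues: "There will be a 'yes' or 'no' answer recorded in the CRF for each criterion in each patient". The only missingness it foresees is a participant who stops or declines the examination. The sample size carries a 10% allowance, and the recruitment target is to be lowered if less than 10% is missing. All criteria then enter a backward logistic model with exit at p = 0.157.

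On who is studied and when, section 5.2.1 admits "New presentation to a specialist clinic (secondary care or community hub) with a vulval skin complaint", with no condition on earlier treatment. Section 4.1 says "Participants will have one study visit that will last approximately 30 minutes" and "There will be no follow up appointments related to the study". Section 6.1 has the research team, not the blinded assessor, record "Treatments received (Y/N and what treatment" together with treatment duration and whether the patient is on active treatment.

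**The concern.** The reason given for complete data does not fit every item on the list. Whether a condition responded to a steroid cannot be seen on examination; it is known only from an earlier course of treatment. A patient who has never had such a course has no response to report, and the single visit cannot generate one. Pain related to sexual activity has the same difficulty in someone who is not sexually active.

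The protocol offers two answers and no rule for these patients. If *no* is recorded, the steroid variable no longer separates responders from non-responders. It separates those who were treated and responded from everyone else, and everyone else includes patients never given the chance to respond. Whether a steroid was prescribed before referral may itself depend on earlier suspicion of LS, so the coefficient can partly reflect prescribing patterns.

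At stake is one of the five critical candidate predictors. Its weight in the tool, and whether backward selection keeps it, would depend partly on how often patients at the recruiting sites had been treated before referral. That may differ in primary care or in self-assessment, where section 1.3 intends the tool to be used.

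**Working it through.** **Are never-treated patients to be expected?** Three features of the protocol say so. Prior steroid use is not an entry condition (5.2.1). Treatment received is itself a yes/no data item (6.1). The rationale says delayed community diagnosis holds back early effective therapy (1.3). Nor can the study observe response in someone who starts treatment at the first consultation: the research visit falls within two weeks of it (5.1), whereas section 1.2 describes remission over three months.

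**The plan's own figure.** 370 × 1.10 = 407, so the recruitment target reproduces. The margin is 407 − 370 = 37 participants (37/407 = 9.1%).

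**What forced coding does to the steroid item.** If never-treated patients are recorded as *no*, then in each group

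P(yes) = P(treated) × P(response given treated),

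and OR = [a/(1 − a)] / [b/(1 − b)], where a and b are P(yes) in LS and non-LS.

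Inputs:
- Response in treated LS: 70%, borrowed from the remission figure in section 1.2. Using it as the chance of a *yes* on this item is an assumption.
- Response in treated non-LS: 30%, assumed.
- Shares treated before the visit: not in the protocol, assumed.

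Results (univariable):
- Treated patients only: a = 0.70, b = 0.30; OR = 2.333/0.4286 = 5.44.
- 40% of both groups treated: a = 0.28, b = 0.12; OR = 0.3889/0.1364 = 2.85.
- 60% of LS and 20% of non-LS treated: a = 0.42, b = 0.06; OR = 0.7241/0.0638 = 11.3.
- 60% and 20% treated, but response uninformative (50% in both groups): a = 0.30, b = 0.10; OR = 0.4286/0.1111 = 3.86. This association comes from prior treatment alone.

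In the 40%/40% case with 185 patients per group, *no* answers number 185 × (0.72 + 0.88) = 296. Of these, 185 × (0.60 + 0.60) = 222, or 75%, come from patients who were never treated.

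**What would happen if not-assessable answers were counted as missing.** More than 37 never-treated patients among 407 would take complete cases below 370. At an assumed 25% never treated, 407 × 0.75 ≈ 305 remain; at 50%, about 203. The 10% allowance was not sized for this, so dropping these patients is not a workable repair.

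No calculation is offered for the sexual-activity item, because the protocol gives nothing on which to base one.

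**The case against.** The strongest reply is that this is a prediction model, not an effect estimate. A variable meaning *has responded to a topical steroid, yes or no* can be fitted validly if it is recorded the same way in use. That stands. The 5.4 is the association among treated patients under the stated assumptions; it is not a true value that the model must recover. What remains is lost information and doubtful transport, and the odds ratios illustrate the mechanism without measuring either. They are also univariable, whereas the planned model is multivariable.

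A second reply is that treatment history is collected for everyone, so an analysis plan could recode the item; the SAP was not available for this review. This stands in part. The steroid item can be recoded if the treatment record is specific enough. The data listed in section 6.1 do not show who is not sexually active, so that item needs a change to the CRF. The yes/no rule and its justification are in any case written into the protocol.

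Several stronger readings are tempting and are not supported:
- *Never-treated patients are coded as non-responders.* The protocol does not say this. It is the natural result of presence/absence recording, but an assessor could also guess *yes*, which would misclassify too.
- *New patients are untreated patients.* They are new to the specialist clinic. Section 6.1 plainly expects some to have had earlier diagnoses and treatment.
- *All the symptom items are affected.* Itch, irritation and pain unrelated to sexual activity are also not examination findings, but any patient can answer them, and section 6.1 lets the assessor ask research questions. Only two items can be inapplicable.
- *The association could reverse.* With 20% of LS and 60% of non-LS treated, a = 0.14, b = 0.18 and OR = 0.74. That needs less prior treatment in LS, the opposite of what prescribing on suspicion of LS would give, and the documents do not point to it.
- *The intended users are untreated people.* Section 1.3 names health professionals and patients, without that restriction.

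**Conclusion.** The point holds for two of the 17 features, and mainly for steroid response because it is a critical item. As written, section 7.1 requires an answer that some participants cannot have, and justifies this by an examination that cannot supply it. Following the rule mixes response with prior prescribing in a predictor that enters the backward selection.

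The size and direction of the effect are not known. They depend on the treated shares in LS and non-LS, which the protocol does not give. Under the assumed response rates, the coded odds ratio is about 2.9 with equal treated shares of 40% and about 11 with shares of 60% and 20%, against 5.4 among the treated. These figures show only that the treated shares can move the coefficient substantially either way. They do not show that it will be distorted by any particular amount, nor that the item will be wrongly kept or dropped.

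**What to change.** 1. Add a not applicable / not assessable option to the CRF for steroid response and for pain related to sexual activity. With no later study visit planned, this has to be captured at the assessment.
2. Using the treatment history already collected, model steroid response in three levels: never treated, treated and responded, treated and did not respond. Report the model with and without this item as a sensitivity analysis.
3. Correct the missing-data paragraph in section 7.1 so that it no longer rests on every feature being assessed by examination.
4. State there that not assessable is a recorded level and not missing data, both for the 10% allowance and for the rule that lowers the recruitment target.

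The cost is one CRF option on two items, some analysis wording, and one extra parameter per affected item in a sample sized for up to nine predictors. The repair is partial: the never-treated coefficient will still partly reflect prescribing patterns, and the report should say so.

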5 SELECTION AND WITHDRAWAL OF PARTICIPANTS

5.1 Recruitment

- Potential participants will be consecutive new patients referred with a vulval skin complaint to a specialist outpatient clinic (types of clinic are detailed in section 3.2).
- They will be identified from clinic lists by the usual care team.
- The study participant information sheet (PIS) will be sent in advance of their outpatient appointment via letter of invitation, or text message with a link to the PIS (depending upon site specific processes for contacting patients).
- Interested patients will complete an online expression of interest form following which the local site research team will contact the patient to answer any questions and discuss potential participation. They can also contact the local site research team via telephone if preferable to the patient (i.e patient doesn't want to click on the link or QR code in the PIS).
- Following discussion with the local site research team, if willing to participate, the patient can complete consent online in advance of their appointment. If not completed in advance, they can complete consent at the time of their face-to-face scheduled clinic appointment.
- On attendance at the face-to-face outpatient appointment:
 - Those **who have already consented** to participate in the study will have consent confirmed by a member of the research team. They will undergo their usual consultation (history and examination) plus a second examination by a blinded trained assessor. Participants who are from the Nottingham centre may also receive a third examination. This is to assess whether two different professionals using the diagnostic criteria agree on the same diagnosis. A member of the research team will collect additional information and enter this onto the CRFs.
 - Those **who have not yet consented** will be given the opportunity to discuss their participation further with a member of the research team. If willing, they will complete online/paper consent and they will go on to have their usual consultation plus a second examination by a blinded trained assessor. Participants who are from the Nottingham centre may also receive a third examination. This is to assess whether two different professionals using the diagnostic criteria agree on the same diagnosis. A member of the research team will collect additional information and enter this onto the CRFs.

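### Section 7.1c labels each of 17 features as having 'good' agreement from a kappa point estimate on 40 participants, which is too imprecise near 0.60; section 5.1 misstates what is compared

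*Protocol*

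**What the plan says.** Section 7.1, part c, fixes three things: the sample, the unit and the criterion. The sample and unit are: "The inter-observer reliability for assessing the individual diagnostic criteria on 20 cases and 20 non-cases from one of the sites will be calculated". The criterion is: "A value of Kappa >60% will be considered acceptable as 'good' agreement between observers". There are two independent assessors, both at Nottingham.

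Section 3.3.1 sets the number of features: "The SHELLS diagnostic test accuracy study is using this list of 17 diagnostic features as the index test". The missing-data paragraph of section 7.1 makes each one binary: "There will be a 'yes' or 'no' answer recorded in the CRF for each criterion in each patient".

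Section 5.1 explains the third examination at Nottingham differently, and does so twice: "This is to assess whether two different professionals using the diagnostic criteria agree on the same diagnosis".

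Section 7.2 justifies 370 (407 with allowance for missing data) for the prediction model. The protocol gives no derivation or target precision for the 40, and does not say what follows for a feature at or below 0.60.

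**The concern.** A kappa from 40 pairs has a wide sampling distribution. Comparing its point estimate with 0.60 treats an estimate just above the mark as established agreement and one just below as a lack of it. The rule is applied 17 times.

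The stake is the published statement of which features two observers can assess consistently. That matters here because section 1.3 intends the tool for non-specialists and patients.

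Two related points concern the same sub-study:

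- The protocol does not say how the 20 cases and 20 non-cases are reached. Case status comes from the managing clinician, whose assessment normally comes first (section 6.1). If third examinations were requested by diagnosis, a request could tell the blinded assessors the status once one group was full.
- Section 5.1 and section 7.1c name different endpoints. Agreement on a diagnosis and agreement on features are not the same quantity.

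**Working it through.** **Inputs from the protocol.** n = 20 + 20 = 40 pairs; two raters; a binary feature; 17 features; criterion kappa > 0.60 (sections 3.3.1 and 7.1). There is no stated precision or error rate to reproduce.

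**Assumptions, shown as ranges.** Feature prevalence p of 10–50%; both raters have the same prevalence; true kappa κ of 0.40–0.80.

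**Model.** Kappa = (po − pe)/(1 − pe), where po is observed and pe chance agreement. With equal margins, each discordant cell has probability p(1−p)(1−κ), 'both yes' has p − p(1−p)(1−κ), and 'both no' has the remainder. All 2×2 tables with n = 40 were enumerated exactly, and the probabilities of those with kappa above 0.60 were summed.

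| Prevalence | κ = 0.40 called good | κ = 0.50 called good | κ = 0.70 misses | κ = 0.80 misses |
|---|---|---|---|---|
| 50% | 6.6% | 20.4% | 22.5% | 3.8% |
| 30% | 8.9% | 23.9% | 22.9% | 5.0% |
| 20% | 11.9% | 27.1% | 25.6% | 7.7% |
| 10% | 20.1% | 34.6% | 29.3% | 14.0% |

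A simulation that held 20 cases and 20 non-cases fixed, with various feature prevalences in the two groups, gave 21–27% at κ = 0.50 and 22–26% at κ = 0.70. The stratified sampling therefore does not change the picture.

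**Precision at κ = 0.60.** Large-sample variance = (1−κ)/n × [(1−κ)(1−2κ) + κ(2−κ)/(2p(1−p))].

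- p = 50%: 0.01 × [−0.08 + 0.84/0.50] = 0.0160; SE 0.126; half-width 1.96 × 0.126 = 0.25; interval about 0.35–0.85.
- p = 20%: 0.01 × [−0.08 + 0.84/0.32] = 0.0255; SE 0.160; half-width 0.31; interval about 0.29–0.91.

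**Effect of one possible two-part rule.** A feature is called good only if kappa exceeds 0.60 and the lower 95% limit exceeds 0.40:

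| Prevalence | κ = 0.50 called good, now → two-part | κ = 0.70 called good, now → two-part |
|---|---|---|
| 30% | 23.9% → 14.1% | 77.1% → 63.5% |
| 20% | 27.1% → 13.8% | 74.4% → 55.1% |
| 10% | 34.6% → 11.3% | 70.7% → 38.0% |

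**The wording conflict.** Sections 3.3.1, 6.1 and 6.2 have the blinded assessor record the presence or absence of features. The synopsis and section 7.1c speak of variability in the criteria. Only section 5.1 speaks of a diagnosis, and none of these sections has the blinded assessors record one.

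**The case against.** The strongest reply is that confidence intervals and agreement indices are reporting details that a statistical analysis plan, not seen here, may contain. That is fair for the intervals themselves. But the 40 participants and the criterion on the kappa value are fixed in the protocol, and reporting an interval beside the label would not change how the label is assigned.

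A second reply is that the error rates rest on assumed prevalence and on true kappas chosen 0.10 from the mark. This stands. At 20–50% prevalence, a feature at 0.40 is called good only about 7–12% of the time and one at 0.80 misses only about 4–8% of the time.

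Several stronger readings are tempting, and the protocol does not support them:

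- *Kappa decides which features enter the tool.* Section 7.1 enters all criteria in the backward regression with exit at p = 0.157, and kappa plays no part in that. The training manual is linked to clinical photographs (sections 5.5 and 6.1), not to kappa.
- *About 4 of the 17 features will be mislabelled.* That expectation (17 × 0.20 to 0.27 = 3.4 to 4.6) needs every feature to lie 0.10 from the mark.
- *Labels are largely a matter of chance.* Even at 0.50 and 0.70 the label is right roughly 73–80% of the time at 20–50% prevalence.
- *Erosions and perianal fissure are rare, so their kappas are unusable.* The protocol gives no prevalence for them.
- *The 20 + 20 design unblinds the assessors.* It would do so only if participants were chosen prospectively by diagnosis. The 40 could instead be drawn afterwards from those examined twice, and sections 6.1 and 6.3 restrict access to the diagnosis.

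**Conclusion.** The point holds as a limited one. Followed as written, section 7.1c attaches a label that 40 pairs cannot support for features whose true kappa is near 0.60. The error is about 20–27% at true kappa 0.50 and about 22–26% at 0.70, with a 95% half-width of about 0.25–0.31 at 0.60. These figures assume 20–50% prevalence and equal rater margins, and both errors rise to about 29–35% at 10% prevalence. The consequence is confined to the reliability conclusion.

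The conflict between sections 5.1 and 7.1c is plain on the text and needs no assumption. The blinding risk is conditional: the protocol leaves the selection of the 40 open, and one way of doing it would be harmful. The change is worth making because it costs almost nothing.

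**What to change.** 1. In section 7.1c, base the statement for each feature on kappa with its 95% confidence interval, plus positive and negative agreement. Report a feature as inconclusive when the interval also covers clearly lower agreement. A lower limit above 0.40 is one option; the cut is a judgement for the study team.
2. Analyse all Nottingham participants who have both blinded examinations. State that third examinations are not requested according to the managing clinician's diagnosis. Section 3.2 expects 50–60% of new patients to have LS, so 40 consecutive participants would include about 20–24 with LS (0.50 × 40 to 0.60 × 40) and a quota gains little.
3. In section 5.1, at both places, say that the third examination assesses agreement on the individual diagnostic features, to match section 7.1c.

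The cost is wording, with no added participants required. The price is more inconclusive results: under the 0.40 option, a true kappa of 0.70 is called good about 63% of the time instead of 77% at 30% prevalence, and about 38% instead of 71% at 10%. The imprecision of 40 pairs remains, but it becomes visible. For scale, holding the present rule's error to 10% at both 0.50 and 0.70 would need about 124–193 pairs at 20–50% prevalence.
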